9.1. Adverse Events

Treatment-emergent AEs are defined as those AEs or SAEs that occur after the start of study drug dosing. All TEAEs will be summarized by treatment group (SYD 101 0.01%, SYD 101 0.03%, or Vehicle) according to treatment taken at the time of event. Adverse events with onset set more than 30 days from date study treatment discontinuation will be summarized separately. In addition, all SAEs, including deaths, will be listed and summarized separately.

For the purpose of inclusion in TEAE tables, incomplete AE start and end dates will be imputed as follows:

Missing onset dates (where UK and UKN indicate unknown or missing day and month respectively):

- UK-MMM-YYYY: If the month and year are different from the month and year of the date of first dose, assume 01-MMM-YYYY. If the month and year are the same as the month and year for the date of first dose, and the end date (after any imputation) is on or after the date of first dose, then assume the date of first dose (Day 1). If the month and year are the same as the date of first dose, and the end date (after any imputation) is prior to the date of first dose, then assume the end date for the start date.
- DD-UKN-YYYY/UK-UKN-YYYY: If the year is different from the year of the date of first dose, assume 01-JAN-YYYY of the collected year. If the year is the same as the date of first dose year, and the end date (after any imputation) is on or after the date of first dose, then assume the date of first dose (Day 1). If the year is the same as the date of first dose, and the end date (after any imputation) is prior to the date of first dose, then assume the end date for the start date.

Missing end dates (where UK and UKN indicate unknown or missing day and month respectively):

- UK-MMM-YYYY: Assume the last day of the month;
- DD-UKN-YYYY/UK-UKN-YYYY: Assume 31-DEC-YYYY

All adverse events will be classified by System Organ Class and Preferred Term (PT) according to the Medical Dictionary for Regulatory Activities (MedDRA, Version 21.0 or higher).

An overview summary of the number and percentage of participants with any TEAE, serious TEAE, treatment-related TEAE, treatment-related serious TEAE, TEAE leading to drug withdrawal, TEAE leading to study discontinuation, and AE leading to death will be provided by treatment group. The overall summaries will be presented for all adverse events, all ocular events, and all non-ocular events.

9.1.1. Incidence of Adverse Events

Summaries that are displayed by system organ class (SOC) and preferred terms will be ordered by descending incidence of SOC and preferred term within each SOC. Summaries displayed by preferred term only will be ordered by descending incidence of preferred term. Incidence summaries will be presented separately for ocular and non-ocular events. For ocular summaries,

a participant will be counted once for the given level of summary if the participant experiences the event in either eye. Summaries of the following types will be presented:

- Overall summary of number of unique TEAEs and treatment-emergent SAEs
- Overall summary of number of unique TEAEs and treatment-emergent SAEs by subgroup (Age, Sex, Race and Iris Color)
- Participant incidence of TEAEs by MedDRA SOC and preferred term
- Participant incidence of TEAEs by MedDRA SOC and preferred term
- Participant incidence of TEAEs by severity grade, MedDRA SOC, and preferred term
- Participant incidence of TEAEs by relationship to study drug, MedDRA SOC, and preferred term
- Participant incidence of severe TEAEs related to study drug by MedDRA SOC and preferred term
- Participant incidence of SAEs by MedDRA SOC and preferred term
- Participant incidence of non-serious AEs by MedDRA SOC and preferred term
- Participant incidence of AEs leading to discontinuation of study drug by MedDRA SOC and preferred term

At each level of summarization (e.g., any AE, SOC, and preferred term), participants experiencing more than one TEAE will be counted only once. In the summary of TEAEs by severity grade, participants will be counted once at the highest severity reported at each level of summarization; in the summary of TEAEs by relationship, participants will be counted once at the closest relationship to study drug. Related events include those reported as “Possibly Related” or “Related” to study drug; events considered not related are those reported as “Unlikely” or “Not Related” to study drug.

At the Month 36 and Month 48 analysis, adverse events will be assigned based on the treatment being taken at the time of the event. If an event occurs after a participant is on escape medication, the event will be assigned to the SYD-101 0.03% treatment group regardless of the randomized treatment.

Additionally, adverse events will be summarized separately for those events with onset after Month 36. Events will be assigned based on the treatment being taken at the time of the event.

Adverse event data will be presented in data listings by participant, treatment group, and event. Serious AEs and AEs leading to discontinuation of the study drug will be presented in separate data listings.

9.1.2. Adverse Events Related to Study Drug

A summary of related TEAEs, either possibly related or related, to study drug will be presented in a table by total number of TEAE and incidence of occurrence. The investigator will provide an assessment of the relationship of the event to the study drug. If a participant reports multiple occurrences of the same TEAE, only the most closely related occurrence will be presented in the incidence count. TEAEs that are missing a relationship will be presented in the summary table

as “Related” but will be presented in the data listing with a missing relationship. Percentages will be calculated out of the number of participants in the Safety set.

The TEAE data will be categorized and presented by SOC, PT, and relationship in a manner similar to that described in Section 9.1.1.

9.1.3. Severity of Adverse Event

A summary of TEAEs by severity will be presented in a table by total number of TEAE and incidence of occurrence. The severity that will be presented represents the most extreme severity captured on the CRF page. The possible severities are “Mild,” “Moderate,” and “Severe.” In the TEAE severity table, if a participant reported multiple occurrences of the same TEAE, only the most severe will be presented in the incidence count. TEAEs that are missing severity will be presented in tables as “Severe” but will be presented in the data listing with a missing severity. Percentages will be calculated out of the number of participants in the Safety set. Additionally, a summary of TEAE related to study drug by severity will be presented.

9.1.4. Serious Adverse Events

Treatment-emergent SAEs will be presented in a table. At each level of participant summarization, a participant is counted once for the incidence if the participant reported one or more events. Percentages will be calculated out of the number of participants in the Safety set. The treatment-emergent SAE data will be categorized and presented by SOC and PT in a manner similar to that described in Section 9.1.1.

9.1.5. Death or Adverse Events Leading to Treatment or Study Discontinuation

All AEs leading to treatment or study discontinuation will be summarized. All discontinuations will be assessed based on data recorded in the AE eCRF page. AEs leading to treatment discontinuation will be identified as AEs where the action taken with study drug is “Drug Withdrawn”. AEs leading to study discontinuation will be identified as AEs where the caused study discontinuation field is marked as “Yes”. In addition, all deaths will be listed. Participant deaths will be identified as AEs where the outcome is “Fatal”.

9.1.6. Adverse Event by Annual Period

A summary of AEs by annual period: Year 1 (Study days 1- 409 inclusive), Year 2 (Study days 410- 773 inclusive), Year 3 (Study days 774- 1137 inclusive), and Year 4 (Study days 1138- 1516 inclusive), will be presented. Each period summary will include AEs occurring in the period, either as a new onset event or a prior event ongoing into the period, including AEs with onset date within the period start and end dates (inclusive), AEs with a start date prior to the period start date and AE stop date after period start date, and AEs with start date prior to period start date and ongoing after period start date. Note, for the Month 24 and Month 36 analyses, the data of the data cut will also be taken into account for ongoing events to ensure that a participant had been followed so that the data cutoff date for the participant would be after the annual period start date. (e.g., if the data cut was taking on date that would be only 28 months of

follow-up for a participant, ongoing AEs for that participant would be counted in the Year 3 annual period but not be included in the Year 4 annual period.)

At each level of participant summarization, a participant is counted once for the incidence if the participant reported on or more events in that period. If an AE is ongoing across multiple periods, it will be counted in each period in which the AE was ongoing. Percentages will be calculated out of the number of Participants in the Safety set. The treatment-emergent SAE data will be categorized and presented by SOC and PT in a manner similar to that described in Section 9.1.1.

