1.3 SCHEDULE OF ACTIVITIES (SOA)

| Study Period | Screening | Part 1: Primary Treatment Period | | | | | | | | | | | | | | Part 2: Randomized Withdrawal | | | | |
|--|--|----------------------------------|------------|-------------|-------------|-------------|-------------|-------------|-------------|-------------|--------------|--------------|--------------|--------------|--------------|-------------------------------|--------------|----------------------|-------|-----------|
| | | Visit | SCR | BL | Week 2 | Mo 3 | Mo 6 | Mo 9 | Mo 12 | Mo 15 | Mo 18 | Mo 21 | Mo 24 | Mo 27 | Mo 30 | Mo 33 | Mo 36 | Mo 39 | Mo 42 | Mo 48/EOS |
| Visit Window | Within 21 days prior to Day 1 ^a | Day 1 ^a | Day 14 ± 3 | Week 13 ± 1 | Week 26 ± 2 | Week 40 ± 2 | Week 52 ± 2 | Week 65 ± 2 | Week 78 ± 2 | Week 91 ± 2 | Week 104 ± 2 | Week 117 ± 2 | Week 130 ± 2 | Week 143 ± 2 | Week 156 ± 2 | Week 169 ± 2 | Week 182 ± 2 | Week 208 ± 2 (or ET) | | |
| Informed Consent/Accent ^b | X | | | | | | | X | | | | | X | | | | X | | | |
| Inclusion/Exclusion Review | X | X | | | | | | | | | | | | | | | | | | |
| Demographics/Med Hx ^c | X | | | | | | | | | | | | | | | | | | | |
| Con Meds/Procedures ^d | X | X | X | X | X | X | X | X | X | X | X | X | X | X | X | X | X | X | X | |
| Adverse Events ^d | X | X | X | X | X | X | X | X | X | X | X | X | X | X | X | X | X | X | X | |
| Vital Signs ^e | X | | | | | | X | | | | X | | | | X | | | | X | |
| Urine Pregnancy Test ^f | | X | | | | | X | | | | X | | | | X | | | | X | |
| Tolerability Questionnaire ^g | | | | X | X | | X | | X | | X | | X | | X | | X | X | X | |
| QOL Questionnaire ^h | | | | | | X | | X | | | | X | | | | X | | | | X |
| BCVA by ETDRS ⁱ | X | X | | X | X | | X | | X | | X | | X | | X | | X | | X | X |
| Binocular Near-BCVA | | X | | | X | | X | | X | | X | | X | | X | | X | | X | X |
| Pupil Diameter | | X | | | X | | X | | X | | X | | X | | X | | X | | X | X |
| Accommodative Amplitude | | X | | | X | | X | | X | | X | | X | | X | | X | | | X |
| Specular Microscopy ^j | | X | | | | | X | | | | X | | | | | | | | | X |
| Biomicroscopy | X | X | | X | X | | X | | X | | X | | X | | X | | X | | X | X |
| IOP ^k | | X | | | | | X | | | | X | | | | X | | | | X | |
| Cycloplegic Autorefraction ^l | X | X | | | X | | X | | X | | X | | X | | X | | X | | X | X |
| Cycloplegic Biometry ^m | X | | | | | | X | | | | X | | | | X | | | | X | |

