4.1. Sample Size

Group sample sizes of 280 in each treatment arm will achieve at least 90% power to detect a difference in the percentage of participants with myopic progression (>0.75 D) of at least 15% between a SYD-101 arm and Vehicle. Power calculations presented in Figure 4-1 are based on the Chi-squared test at a 2-sided significance level of 0.025.

[figure not shown]
Figure 4-1 Power for 2-Sided Chi-Square Test Evaluated at Alpha=0.025 for Proportion Responders When 280 Participants Per Arm

Additionally, group sample sizes of 280 per treatment arm achieves >90% power to detect a reduction of 0.18 D or more in the annual progression rate between SYD-101 and Vehicle, assuming a common SD of 0.60 D. Power calculations presented in

Figure 4-2 are based on a 2-sample t-test evaluated at the 0.025 significance level.

Figure 4-2 Power for 2-Sided T-Test Evaluated at Alpha=0.025 for Annual Progression Rate When 280 Participants Per Arm

Furthermore, to estimate the statistical power of the two region- specific primary endpoints, simulations based on various assumptions regarding the mean vehicle annual progression rate, the mean active annual progression rate based on % reduction from the vehicle annual progression rate, the SD for the APR as well as allowing for participant dropout/study treatment discontinuation and escape medication have been considered to investigate statistical power for a range of sample sizes. Simulations were run after the protocol was finalized to assess protocol sample size assumptions. For the most likely assumption of parameters examined, a mean placebo/control APR of 0.65 D and a mean active APR 0.325 D (a 50% reduction from the mean vehicle/control APR) both with a SD of 0.55 D and an annual dropout/study treatment discontinuation rate of 7%, a sample size of 217 participants per treatment arm provides an approximate 97% power for the FDA endpoint and an approximate 99.96% power for the EMA endpoint assuming a significant level of 0.025.

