4.3.3. Safety set

The Safety set will include all participants who receive any amount of study drug (SYD-101 0.01%, SYD-101 0.03%, or Vehicle). The Safety set will be the primary population used for safety analyses. Treatment assignment will be based on the treatment actually received. Participants who receive one incorrect treatment kit but whose treatment is corrected to their randomized treatment at the next treatment dispensation will be included in all analyses as receiving the correct treatment.

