For safety analyses from baseline to Month 24, the baseline will be considered the start of study prior to dose of any study medication. Unless otherwise specified, for safety analyses at Month 36, at Month 48, or from Month 36 to Month 48, data will be summarized based on treatment being taken at the time of event occurrence/assessment, including those who take SYD 101 0.03% as escape medication or who are re-randomized to Vehicle at Month 36. Participants who receive escape medication or who are re-randomized at Month 36 will be included under each treatment received during the analysis period. Percentages, if applicable, will be calculated based on the number of participants in the Safety Set who received at least one dose of the given treatment. For each treatment received, the baseline value will be the last non-missing assessment prior to initiation of the given treatment. (For participants originally randomized to SYD 101 0.03%, who are rerandomized to Vehicle at Month 36, and then subsequently switch to open label SYD 101 0.03% as escape medication, assessments made on SYD 101 0.03% will use the last non-missing value on or prior to Day 1/date of first SYD 101 0.03% treatment as baseline.) Total summaries will include data from assessments during the first 24 months while participants should be on their original randomized treatment only.

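### The yearly AE percentages in SAP 9.1.6 cannot be compared across years: the periods differ in length, the denominator never shrinks, and ongoing AEs are recounted

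*SAP*

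**What the plan says.** SAP 9.1.6 divides the study into "Year 1 (Study days 1- 409 inclusive), Year 2 (Study days 410- 773 inclusive), Year 3 (Study days 774- 1137 inclusive"), followed by "Year 4 (Study days 1138- 1516 inclusive"). Within each period a participant counts once per level of summary. The numerator takes both AEs that start in the period and AEs carried into it: "If an AE is ongoing across multiple periods, it will be counted in each period in which the AE was ongoing".

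The denominator is the same throughout: "Percentages will be calculated out of the number of Participants in the Safety set". SAP 4.3.3 defines that set by first exposure: "The Safety set will include all participants who receive any amount of study drug". Nobody leaves it later.

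Two other rules bear on this.

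- The opening text of SAP Section 9 sets a general denominator for the Month 36 and Month 48 safety analyses, "based on the number of participants in the Safety Set who received at least one dose of the given treatment". This depends on treatment ever received, not on being followed in a given period.
- A note in 9.1.6 checks that a child's data cut falls after the start of a period before an ongoing AE is counted there. It governs the numerator only.

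**The concern.** A table of AEs by year of dosing invites the reader to look along the row. On long-term treatment of children, the natural question is whether tolerability changes with time. A row can be read that way only if each column gives the participants the same chance of contributing an event.

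Here Year 1 is 45 days longer than Years 2 and 3. Children who have left stay in the later denominators, although Protocol 8.3.4 ends AE collection on the last day of participation. Both features push later new-onset percentages down. Recounting ongoing AEs pushes later percentages up. The net trend therefore mixes artefacts of opposite sign with any real change, and the table as planned cannot separate them.

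**Working it through.** **Period lengths.** 409 − 0 = 409; 773 − 409 = 364; 1137 − 773 = 364; 1516 − 1137 = 379 days. The cut points equal the upper limits of the Month 12, 24, 36 and 48 windows in SAP Table 4-1. The documents state no AE rate or expected trend, so there is no plan figure to reproduce beyond these boundaries.

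**Length alone, new-onset AEs, constant rate, no loss.** Years 2 and 3 against Year 1: 364/409 = 0.89, about 11% lower.

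**Adding loss.** The only rate in the documents is in SAP 4.1: "an annual dropout/study treatment discontinuation rate of 7" percent. With annual loss d, λ = −ln(1 − d)/365.25 per day. Expected observed days per Safety-set participant in a period from s to e are (exp(−λs) − exp(−λe))/λ. At d = 0.07, λ = 0.0001987, giving:

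| Period | Observed days per participant | Ratio to Year 1 |
|---|---|---|
| Year 1 (0 to 409) | 392.8 | 1.00 |
| Year 2 (409 to 773) | 323.7 | 0.82 |
| Year 3 (773 to 1137) | 301.1 | 0.77 |

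For d of 3%, 5% and 10%, the Year 3 ratio is 0.84, 0.80 and 0.72. That is 16% to 28% lower, with 23% at the planning value.

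**Participants counted once.** The ratios above suit uncommon AEs. At 7% loss, an AE with rate 0.05 per year gives 5.2% in Year 1 and 4.0% in Year 3 (23% lower). A very common one at 1.5 per year gives 79% and 65% (18% lower).

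**Adding the recount.** With mean AE duration D, the AEs already ongoing at the start of a period add D × (1 − exp(−s/D)) × exp(−λs) to the observed days above; the AE rate cancels in the ratio. For Year 3, s = 773 and exp(−λs) = 0.858. The durations are assumptions:

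| Mean duration D | Added to 301.1 | Year 3 / Year 1 |
|---|---|---|
| 14 days | 12.0 | 0.80 |
| 60 days | 51.5 | 0.90 |
| 180 days | 152.3 | 1.15 |

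The direction therefore depends on how long the AEs last.

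**Why Year 4 gets no single figure.** Over its nominal 379 days the new-onset ratio at 7% loss is 0.74. The last visit is at Week 208, 208 × 7 = day 1456, so only about 1456 − 1137 = 319 days are normally observed, and the ratio becomes 0.63. Treatments also change at Month 36, and SAP 9.1.1 assigns events to the treatment taken at the time. To illustrate, assume the same AE rate on every treatment, equal arms, no escape, the nominal window and denominators fixed at original arm size. Then 0.01% keeps half its children (0.5 × 0.741 = 0.37), 0.03% keeps half and gains the Vehicle arm (1.5 × 0.741 = 1.11), and Vehicle receives half of each active arm (0.74).

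**What removes the artefact.** At 7% loss:

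- Participants at risk at period start, with the SAP's windows, still give 0.89 in Years 2 and 3.
- Equal 364-day windows with the full Safety set still give 0.93 and 0.865.
- Events divided by observed person-time give 1.00 in every year for new-onset AEs.

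**The case against.** The cut points are deliberate. They align the AE years with the visit windows, so they should not be called a slip. The table is descriptive, no test is attached to it, and 9.1.6 does not state that its purpose is to show a trend. All arms share the same windows, so comparing arms within a year remains fair before treatments change, provided loss is similar across arms. The SAP also plans useful context: exposure and the number on each treatment per visit (7.3.1), disposition (5.1), a separate summary of AEs starting after Month 36 (9.1.1) and tolerability by visit (9.3.9). All of this stands. None of it changes the percentages in this table, and a reader would have to redo the division by hand.

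A reader might go further and infer that a constant AE rate will appear to fall by about a quarter over the study. The documents do not support that. The figure applies only to new-onset events, whereas this table also recounts ongoing ones. It depends on the 7% rate, which is a simulation assumption combining dropout with stopping treatment; Protocol 7.1 keeps children who stop the drug in the study, so loss to AE follow-up may be smaller. Nor can one fall be claimed for Year 4 in every arm.

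**Conclusion.** The point holds as one of comparability. Followed exactly, SAP 9.1.6 produces yearly percentages that would differ even if nothing about tolerability changed. For uncommon new-onset AEs at a constant rate, Years 2 and 3 come out about 11% below Year 1 from period length alone, and Year 3 about 23% below at an assumed 7% annual loss (16% to 28% for 3% to 10%). These figures take all participants together, assume exponential loss, and use the full Year 3 window. By arm they would also be affected by escape from Month 24 and by re-randomization at target day 1092, which is 45 days before Year 3 closes. The size and sign of the net trend after recounting depend on AE duration, which the documents do not give.

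The consequence is limited to one descriptive safety table. No efficacy conclusion and no overall AE incidence table changes.

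**What to change.** In SAP 9.1.6:

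- Take as denominator the participants still in follow-up during the period and, at the Month 36 and Month 48 analyses, on the given treatment. State how this relates to the general denominator rule in Section 9.
- Report new-onset events per 100 participant-years of observed follow-up in each period. The existing cut points can then stay, because person-time absorbs the unequal lengths and the early end of Year 4.
- Show new-onset AEs and AEs ongoing from an earlier period in separate columns.

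No new data are needed. The cost is a little more table programming.

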9.1.7. Adverse events after Treatment Discontinuation

All AEs after more than 30 days after the date of last dose of study treatment discontinuation will be presented in a table. At each level of participant summarization, a participant is counted once for the incidence if the participant reported on or more events. Percentages will be calculated out of the number of Participants in the Safety set. The treatment-emergent SAE data will be categorized and presented by SOC and PT in a manner similar to that described in Section 9.1.1. All AEs after treatment discontinuation data by participant will be presented in a listing.

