7 STUDY DRUG DISCONTINUATION AND PARTICIPANT DISCONTINUATION OR WITHDRAWAL FROM STUDY

7.1 DISCONTINUATION OF STUDY DRUG

Discontinuation from study drug does not mean discontinuation from the study, and remaining study procedures should be completed as indicated by the study protocol. If a clinically significant finding is identified (including, but not limited to changes from baseline) after enrollment, the investigator or qualified designee will determine if any change in participant management is needed. Any new clinically relevant finding will be reported as an AE.

The data to be collected at the time of study intervention discontinuation will include the procedures as listed in the schedule of activities.

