8.3.4 TIME PERIOD AND FREQUENCY FOR EVENT ASSESSMENT AND FOLLOW-UP

Any medical condition that is present at the time that the participant is screened will be considered as medical history and not reported as an AE. However, if the study participant's condition deteriorates at any time after the time of informed consent, it will be recorded as an AE.

Changes in the severity of an AE will be documented in the source and eCRF to allow an assessment of the duration of the event at each level of severity to be performed. Adverse events characterized as intermittent require documentation of onset and duration of each episode.

The collection of AEs and SAEs will commence from the time the ICF is signed and continue until the last day of study participation. Events will be followed for outcome information until resolution or stabilization during the study or continue until 7 days (for non-serious AEs) or 30 days (for SAEs) after the last day of study participation.

Adverse events will be monitored throughout the study beginning at the time of informed consent. At each post-Screening visit, the investigator will begin by querying for AEs by asking each participant a general, non-directed question, such as "How have you been feeling since the last visit?" Directed questioning and examination will then be done as appropriate. If the participant presents a potential AE during a telephone visit, the participant will come to the clinic for an unscheduled visit to assess the potential AE. All reported AEs will be documented on the appropriate page of the eCRF, including seriousness, severity, relationship to study drug, action taken, and outcome (including date of resolution or stabilization, if AE is not ongoing). If AEs occur, the first concern will be the safety of the study participants.

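### Adverse events more than 30 days after the last dose are expressed only as a percentage of the whole Safety set, so the figure is not an off-drug risk and moves with each arm's stopping and retention rates

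*SAP*

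**What the plan says.** SAP 9.1.7 defines the table: "All AEs after more than 30 days after the date of last dose of study treatment discontinuation will be presented in a table". Each participant is counted once per level of summary. The denominator follows: "Percentages will be calculated out of the number of Participants in the Safety set". A participant listing is also planned.

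SAP 4.3.3 defines that denominator: "The Safety set will include all participants who receive any amount of study drug". It therefore includes children who never stop. For the Month 36 and Month 48 safety analyses, the opening text of SAP Section 9 narrows percentages to those "calculated based on the number of participants in the Safety Set who received at least one dose of the given treatment", which still does not require that a child has stopped.

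Two protocol rules determine who can appear in the numerator. Section 7.1 says "Discontinuation from study drug does not mean discontinuation from the study", so children who stop are meant to stay under observation. Section 8.3.4 sets the end of collection: "The collection of AEs and SAEs will commence from the time the ICF is signed and continue until the last day of study participation".

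Protocol 9.4.4 asks only for a separate summary of these late events and gives no denominator.

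**The concern.** A child still taking drug at the cut-off cannot have an event more than 30 days after the last dose. A child who leaves the study within 30 days of the last dose cannot have one recorded. Both are in the denominator, and neither is at risk of being counted.

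A reader who takes the percentage as the risk of an adverse event after coming off drug will read it too low. A reader who compares arms may see a difference that comes only from unequal stopping or retention, or miss a real one that unequal retention hides. Unequal stopping is possible here, because the arms are two atropine strengths and a vehicle and some children will stop for related adverse events.

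The SAP handles observation time more carefully elsewhere. Its default denominator in Section 4 is participants with available data, unless otherwise noted. In the annual-period table (9.1.6) it checks that a participant had been followed into a period before counting an ongoing event there. Section 9.1.7 has no comparable step.

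**Working it through.** **The plan's own figures.** The documents state no off-drug event rate, so there is none to reproduce. The only stopping figure is in SAP 4.1, among the inputs to a power simulation: "an annual dropout/study treatment discontinuation rate of 7" per cent. The power stated there for the EMA endpoint is about 99.96% with 217 per arm, means of 0.65 and 0.325 D/year, SD 0.55 D and a 0.025 level. A two-sided two-sample calculation gives 99.995% at 217 per arm and 99.975% at 217 × 0.93² = 187.7 per arm, consistent with the stated value. The 97% for the FDA endpoint comes from a simulation whose model is not given, and was not reproduced. Neither figure shows that 7% is the rate at which children will stop drug.

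**Formula.** Let s be the share of the Safety set that stopped drug and was followed more than 30 days, and r the risk among those children.

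- Reported percentage = s × r
- Factor by which it falls below r = 1/s

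**At 7% per year, compounding, every stopper followed:**

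| Analysis | s | Children per 280 | 1/s |
|---|---|---|---|
| Month 24 | 1 − 0.93² = 13.5% | 38 | 7.4 |
| Month 36 | 1 − 0.93³ = 19.6% | 55 | 5.1 |
| Month 48 | 1 − 0.93⁴ = 25.2% | 71 | 4.0 |

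**Variations (Months 24, 36, 48):**

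- Leaving out those who stopped in the last 30 days, s = 1 − 0.93^((T − 30)/365.25), with T the SAP Table 4-1 target day (728, 1092, 1456): 7.7, 5.3, 4.1.
- Linear accrual, s = 14%, 21%, 28%: 7.1, 4.8, 3.6.
- Half of stoppers stay in follow-up (assumed), s halved: 14.8, 10.2, 7.9.
- Assumed 5% per year, all followed: Month 36, 1/(1 − 0.95³) = 7.0; Month 48, 5.4.
- Assumed 10% per year, all followed: Month 36, 1/(1 − 0.90³) = 3.7; Month 48, 2.9.

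A factor of 5 or more needs s ≤ 20%. At 7% per year that holds at Month 24 and only just at Month 36. At Month 48 it needs no more than 0.20/0.252 = 79% of stoppers to stay in follow-up.

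**Dependence on arm.** Purely as an illustration, take the same off-drug risk of 30% in two arms, with 10% of one arm and 20% of the other off drug and followed. The table shows 0.10 × 30% = 3% against 0.20 × 30% = 6%.

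**The case against.** The Safety-set percentage is not a miscalculation. It is the share of treated children who had a late off-drug event, on the same denominator as most neighbouring adverse-event tables. Section 9.1.7 neither calls it an off-drug risk nor plans a test on it. That stands: what is missing is the second denominator, and the existing percentage should be kept.

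The main withdrawal question is also addressed elsewhere. At Month 36, SYD-101 children not on escape medication are re-randomized 1:1 to continue or to switch to Vehicle (SAP 4.2). Events after Month 36 are summarized separately by treatment at the time (SAP 9.1.1), over those who received that treatment. That is a masked, randomized comparison and it lowers the stakes here. It does not cover children who stop early and take nothing.

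Partial recovery is possible, since disposition (SAP 5.1) gives the number who discontinued treatment and 9.1.7 plans a listing. But no table gives the number followed more than 30 days after the last dose, which is the denominator needed.

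Finally, a denominator limited to stoppers who stayed conditions on two events after randomization, so comparing arms on it is not a randomized comparison. This is correct, and it is why the new figures should supplement the existing percentage and carry that caveat.

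**Conclusion.** The concern holds as one about interpretation. As specified, the percentage in 9.1.7 cannot be read as an off-drug risk, and it varies with each arm's stopping and retention even when the off-drug risk is equal.

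Its size rests on the 7% per year planning assumption and on complete follow-up of stoppers: about 7-fold below the off-drug risk at Month 24, 5-fold at Month 36 and 4-fold at Month 48. Worse retention raises these factors; a higher stopping rate lowers them.

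A reader might infer from the Month 24 and Month 36 values that the shortfall is at least five-fold. The documents do not support a floor: Month 48 gives 4.0, linear accrual gives 4.8 at Month 36, and 10% per year gives 3.7 there. Nor do they support a claim that the arms will in fact differ, since no arm-specific stopping rate is given and the 3% against 6% example is hypothetical.

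This is one descriptive safety table. No endpoint, test or decision rule depends on it. The change is worth making because it is cheap.

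**What to change.** In SAP 9.1.7, keep the Safety-set percentage, labelled as the share of treated children affected, and add for each arm:

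- the number of Safety set participants who discontinued study drug and were followed more than 30 days after the last dose;
- the percentage with an event on that denominator;
- events per 100 person-years of observed follow-up beyond 30 days after the last dose, ending at the last day of participation or the analysis cut-off.

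Add a footnote that this subset is defined by stopping and retention after randomization, so comparisons between arms are descriptive. State also which treatment column holds these events: SAP 9.1 assigns events by treatment taken at the time, and these children are taking none.

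The cost is a sentence or two of SAP text and extra rows in one table shell. The numerator already needs the last-dose date; the only addition is the end of follow-up, so no new data collection is required. The price is small, imprecise denominators: at the planning rate, at most about 38, 55 and 71 children per arm of 280 at Months 24, 36 and 48.
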